9.5. Study size

9.5.1. Self-controlled Risk Interval (SCRI) Design

Because an SCRI design will be used, statistical power for general safety events depends on the total number of events in the risk and control intervals combined, the ratio of the duration of the risk and control intervals, and the IRR. Table 8 presents the statistical power that can be obtained for a range of incidence rate ratios and sample sizes, for a 2-sided alpha = 0.05 level test, using an SCRI design with risk and control intervals of equal duration ([Musonda et al., 2006](#)). For example, 80 events will provide 86% power to detect incidence rate ratios equal to or greater than 2.0.

Table 8. Study size calculations for self-controlled risk interval design

Total events	Incidence rate ratio	Power
20	1.4	0.11
	1.6	0.17
	1.8	0.25
	2.0	0.32
	2.2	0.39
	2.4	0.46
40	1.4	0.18
	1.6	0.31
	1.8	0.44
	2.0	0.57
	2.2	0.68
	2.4	0.76
80	1.4	0.32
	1.6	0.55
	1.8	0.73
	2.0	0.86
	2.2	0.93
	2.4	0.97
100	1.4	0.39
	1.6	0.64
	1.8	0.83
	2.0	0.93
	2.2	0.97
	2.4	0.99

090177e19f732934\Approved\Approved On: 14-Dec-2023 13:35 (GMT)

9.5.2. Study size for the pregnancy cohort

Table 9 provides power calculations for pregnancy outcomes assuming a log-rank test at a 2-sided alpha = 0.05 level for various hazard ratios and numbers of pregnant women (1:1 matching ratio) for each birth outcome assuming the incidence of each outcome is 0.5% for stillbirths, 10% for preterm, and 12% for spontaneous abortion.

Table 9. Power for varying hazard ratios and study size for pregnancy outcomes

Outcome (incidence)	Number of pregnant women per group	Hazard ratio			
		1.2	1.6	2	2.4
Stillbirths (0.5%)	20,000	0.269	0.959	1.000	1.000
	40,000	0.475	0.999	1.000	1.000
	60,000	0.642	1.000	1.000	1.000
	80,000	0.765	1.000	1.000	1.000
	100,000	0.851	1.000	1.000	1.000
Preterm (10%)	20,000	1.000	1.000	1.000	1.000
Spontaneous abortion (12%)	20,000	1.000	1.000	1.000	1.000

For example, assuming the true HR = 1.2, an outcome (eg, stillbirth) with a rate of 0.5% during follow-up, and a sample size of 100,000 per group, there would be 85% power to reject a null hypothesis of HR = 1.0. A sample size of 20,000 per group provides a power of 100% for preterm and spontaneous abortion if the true HR is 1.2 or higher.

For the birth outcomes (i.e., small size for gestational age and major congenital malformations), assuming the true odds ratio = 1.2, an outcome rate of 3% in the unexposed group and a sample size of 20,000 per group, there would be 90% power to reject (at p = 0.05 level for a 2-sided test) a null hypothesis that the prevalence odds ratio = 1.0.

9.6. Data management

[figure not shown]
HPHCI, located in Boston, Massachusetts, will serve as the coordinating center for the study. HPHCI staff or contractors will be responsible for writing and distributing SAS programs that can be used to evaluate the data included in databases at participating data RPs. The distributed network will allow data RPs to maintain physical and operational control of their data while allowing use of the data to meet the study needs. HPHCI will maintain a secure, distributed, querying web-based portal to enable secure distribution of analytic queries, data transfer, and document storage. The system will meet all required state and federal security guidelines for health data (eg, Federal Information Security Management Act of 2002 [FISMA], Health Insurance Portability and Accountability Act of 1996) and will be specifically FISMA compliant for FISMA security controls as specified in the National Institute of Standards and Technology (NIST) Special Publication 800-53 (NIST, 2020).

The RPs will establish and maintain the administrative, hardware, and software capabilities and capacity to respond to data requests in a timely manner. RPs will also provide data science support with epidemiologic review.

090177e19f732934\Approved\Approved On: 14-Dec-2023 13:35 (GMT)

The general analytic workflow is depicted in Figure 4. First, the study coordinating center (at HPHCI) will submit a computer program designed to meet the needs of the study to each participating data RP via a secure portal. Next, the participating RPs will receive and run the computer program behind their firewalls, using data formatted to the SCDM. Then, the RPs will review the aggregate analysis results and return them to the study coordinating center through a secure portal. Next, the study coordinating center will review and aggregate the results across the RPs. As a final step, the aggregated results will then be transferred to the study team, including extended researchers and the study sponsor.

Figure 4. General analytic workflow

HPHCI = Harvard Pilgrim Health Care Institute.

9.7. Data analysis

Analyses will initially be conducted separately using data from each RP. RP-specific aggregated results will be sent to the study coordinating center, which will combine aggregated results across the RPs for reporting. Pooled analysis of incidence rate ratios, HRs, and odds ratio estimates from all RPs will be conducted using privacy-preserving summary-level data sets (eg, risk set-level data sets) or another appropriate method.

Detailed methodology for summary and statistical analyses of data collected in this study will be documented in the SAP, which will be dated, filed, and maintained by the sponsor. The SAP may modify the plans outlined in the protocol; any major modifications of primary endpoint definitions or their analyses would be reflected in a protocol amendment.

Table 10 presents a summary of planned analyses. Analyses are described in more detail in Sections 9.7.1, 9.7.2, 9.7.3, 9.7.4, and 9.7.5.

PFIZER CONFIDENTIAL

CT24-WI-GL02-RF02 4.0 Non-Interventional Study Protocol Template For Secondary Data Collection Study
01-Jun-2022

Table 10. Summary of planned analyses

Type of safety event	Analysis	Study design	Results	Notes on main purpose of analysis/difference from primary analysis
General safety events	Primary analysis	SCRI	Descriptive, IRRs	N/A
	Subgroup analyses in populations of interest: immunocompromised individuals, pregnant women, individuals with severe COVID-19, and subgroups defined by age; additional analysis to be performed in subgroups defined jointly by sex and age (for myocarditis/pericarditis only)	SCRI	Descriptive, IRRs	Subgroup analyses
	Subgroup analysis: by receipt of Pfizer-BioNTech bivalent COVID-19 Vaccine as a primary series vs booster dose	SCRI	Descriptive, IRRs	Exploratory subgroup analysis; only to be performed if feasible
	Sensitivity analysis: alternative risk periods	SCRI	IRRs	Sensitivity analysis to address potential risk interval misspecification; to be performed for general safety events that have signaled in other studies and for which risk intervals are not well characterized
	Sensitivity analysis: quantitative bias analysis to correct comparative risk estimates for outcome misclassification	SCRI	IRRs	Sensitivity analysis to address potential misclassification of outcomes in claims data; to be implemented for myocarditis/pericarditis, if the algorithm is demonstrated to have inadequate performance in other validation studies. Such analysis may also be considered for other general safety events that have signaled in other studies.

090177e19f732934\Approved\Approved On: 14-Dec-2023 13:35 (GMT)

Table 10. Summary of planned analyses

Type of safety event	Analysis	Study design	Results	Notes on main purpose of analysis/difference from primary analysis
Pregnancy and birth outcomes	Primary analysis	Cohort: exposed vs unexposed	Descriptive; IRRs or HRs; PORs	N/A
	Subgroup analyses in populations of interest (immunocompromised individuals, individuals with history of severe COVID-19, and among subgroups defined by age)	Cohort	Descriptive, IRRs or HRs; PORs	Subgroup analyses
	Sensitivity analysis: restrict to population with linkages to immunization registries	Cohort: exposed vs unexposed	IRRs, PORs	Sensitivity analysis to address potential misclassification of unexposed status due to incomplete capture of COVID-19 vaccines in claims data; only to be performed if feasible
	Sensitivity analysis: quantitative bias analysis to correct comparative risk estimates for exposure misclassification	Cohort: exposed vs unexposed	IRRs, PORs	Sensitivity analysis to address potential misclassification of unexposed status due to incomplete capture of COVID-19 vaccines in claims data; to be considered if exposure misclassification is not sufficiently addressed in other analyses
	Sensitivity analysis: restrict to pregnant women who have a recorded history of monovalent COVID-19 vaccine before the index date	Cohort: exposed vs unexposed	IRRs, PORs	Sensitivity analysis to address potential confounding and misclassification of unexposed status in claims data
	Sensitivity analysis: quantitative bias analysis to correct comparative risk estimates for outcome misclassification	Cohort: exposed vs unexposed	IRRs, PORs	Sensitivity analysis to address potential misclassification of outcomes in claims data; analysis to be considered for pregnancy and birth outcomes that have signaled in other studies.

COVID-19 = coronavirus disease 2019; IRR = incidence rate ratio; N/A = not applicable; POR = prevalence odds ratio; SCRI = self-controlled risk interval.

090177e19f732934\Approved\Approved On: 14-Dec-2023 13:35 (GMT)

PFIZER CONFIDENTIAL

CT24-WI-GL02-RF02 4.0 Non-Interventional Study Protocol Template For Secondary Data Collection Study

01-Jun-2022

Page 43 of 62

9.7.1. Analysis of general safety events

For analysis of general safety events (which will be assessed using an SCRI design), Pfizer-BioNTech bivalent COVID-19 vaccinees within each outcome-specific analysis set will be described using demographics, comorbidities, and other key characteristics. For each general safety event, conditional Poisson regression or another appropriate statistical method will be used to obtain incidence rate ratios and 95% CIs in the risk interval compared with the control interval.

9.7.2. Analysis of pregnancy and birth outcomes

Among pregnant women, the distribution of demographics, comorbidities, and other potential confounders will be reported and compared between the matched exposed and unexposed cohorts. Covariate balance in the matched and weighted cohorts will be assessed using standardized differences or other suitable methods.

Vaccinated pregnant women will be matched to pregnant unexposed comparators in a ratio of exposed:unexposed of at least 1:1 on maternal age, US state (if feasible, or broader geographic region if not feasible), and pregnancy start (to address confounding by calendar time). Confounding by other variables will be addressed using inverse probability of treatment weighting, based on propensity scores estimated in the matched population.

In each data RP, measures of incidence or prevalence of pregnancy and birth outcomes and associated 95% CIs will be estimated within the matched exposed and unexposed cohorts.

Cox models or Poisson regression will be used to calculate adjusted HRs or incidence rate ratios and 95% CIs for spontaneous abortion, stillbirth, and preterm birth. For major congenital malformations and small size for gestational age, logistic regression will be used to estimate PORs and 95% CIs.

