Among pregnant women, a cohort design will be used to compare the incidence of pregnancy outcomes (spontaneous abortion, stillbirth, and preterm birth) among those who were exposed to Pfizer-BioNTech bivalent COVID-19 Vaccine during pregnancy compared with that among those who were unexposed to any COVID-19 vaccine during pregnancy (Figure 2). Similarly, a cohort design will be used to compare the prevalence of birth outcomes (major congenital malformations and small size for gestational age) in infants who were born to pregnant women who were exposed to Pfizer-BioNTech bivalent COVID-19 Vaccine during pregnancy compared with that in infants born to pregnant women who were unexposed to any COVID-19 vaccine during pregnancy (Figure 3). Exposed and unexposed pregnant women will be matched on estimated pregnancy start (date of last menstrual period [LMP]), gestational age at cohort entry (for pregnancy outcomes only), maternal age, and US state (if feasible, or broader geographic region if not feasible). Inverse probability of treatment weighting will be used to account for additional confounders.

[figure not shown]
090177e19f732934\Approved\Approved On: 14-Dec-2023 13:35 (GMT)

Figure 2. Cohort design to assess pregnancy outcomes

COVID-19 = coronavirus disease 2019; LMP = date of last menstrual period.

Figure 3. Cohort design to assess birth outcomes

COVID-19 = coronavirus disease 2019; LMP = date of last menstrual period.

A strength of a cohort design with concurrent unexposed comparators is that, unlike the SCRI design, it can be used to study safety events for which the risk varies substantially over time (such as spontaneous abortion) and/or for which the timing of onset is unknown (such as major congenital malformations and small size for gestational age). The use of a contemporaneous comparator rather than a historical comparator avoids bias due to temporal trends in coding for outcomes. Limitations of the cohort approach include the potential for bias due to misclassification of exposed individuals as “unexposed” comparators and bias due to confounding when comparing exposed with unexposed pregnant women.

Confounding will be handled by matching and inverse probability of treatment weighting.

To assess the feasibility for planned analyses, a monitoring analysis will be conducted to describe vaccine utilization among the overall population, among immunocompromised

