9.3.3. Covariates

Table 7 presents variables that will be used for descriptive analysis in analyses of general safety events as well as variables that will be used for descriptive analysis, matching, and

090177e19f732934\Approved\Approved On: 14-Dec-2023 13:35 (GMT)

propensity score estimation in analysis of pregnancy and birth outcomes. These variables will be identified using claims or electronic health records data (where available).

Table 7. Covariates used for descriptive analysis, matching or propensity score estimation

Variable	General safety events	Pregnancy and birth outcomes		
	Descriptive	Descriptive	Matching	Propensity scores
Age (as of the index date or LMP ^a)	X	X	X	
Sex	X			
Geographic region (based on the most recent information at the time of data refresh)	X	X	X	
Immunocompromising conditions (in the 12 months before the index date) 
 Including immunodeficiencies, immunosuppressant medication use, HIV and other immunosuppressing conditions, and receipt of organ or bone marrow transplants 	X	X		X
Pregnancy status as of the index date	X			
History of severe COVID-19 disease (as of the index date) 
 Defined with inpatient diagnoses in the principal diagnosis position or in pregnant women, with inpatient claims with a principal diagnosis of viral diseases complicating pregnancy and a diagnosis of COVID-19 in another position 	X	X		X
Receipt of the index Pfizer-BioNTech COVID-19 bivalent Vaccine as a primary series dose vs booster dose; only to be assessed if feasible to identify in the data sources; anticipated to be incomplete	X	X		
Other vaccines recommended for routine use (on the index date or from 28 days before pregnancy until end of pregnancy) ^b	X	X		X
Estimated pregnancy start date (LMP)		X	X	
Gestational age on the index date ^c		X		

090177e19f732934\Approved\Approved On: 14-Dec-2023 13:35 (GMT)

Table 7. Covariates used for descriptive analysis, matching or propensity score estimation

Variable	General safety events	Pregnancy and birth outcomes		
	Descriptive	Descriptive	Matching	Propensity scores

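### The propensity score leaves out the matching variables, so weighting the matched pregnancy cohorts can reintroduce imbalance on them

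*Protocol*

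**What the plan says.** Section 9.7.2 matches vaccinated to unexposed pregnant women on maternal age, state or region, and pregnancy start, and then states: "Confounding by other variables will be addressed using inverse probability of treatment weighting, based on propensity scores estimated in the matched population". Section 9.1 gives weighting the same residual role: "Inverse probability of treatment weighting will be used to account for additional confounders".

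Table 7 (Section 9.3.3) has separate columns for matching and for propensity scores:

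- Age, the row "Geographic region (based on the most recent information at the time of data refresh", and the pregnancy start date (LMP) are marked for matching; their propensity-score cells are blank.
- "Gestational age on the index date" is marked descriptive only. A footnote limits it to pregnancy outcomes.
- Comorbidities, healthcare utilization, current-pregnancy complications and teratogenic medications are in the score. For the last two, a footnote limits the score to information up to the index date, apart from multiple pregnancy.

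Section 9.1 lists "gestational age at cohort entry (for pregnancy outcomes only" among the matching variables, and Table 1 aligns it by giving each unexposed woman the gestational age at which her match was vaccinated. Table 7 does not mark it for matching.

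The outcome models in Section 9.7.2 are Cox or Poisson for pregnancy outcomes and logistic for birth outcomes. Balance is to be checked by standardized differences in the matched and weighted cohorts.

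**The concern.** Matching makes exposure independent of the matching variables in the matched set as a whole. Weights built from a score that contains only other covariates keep that balance if exposure and the matching variables are also independent given those covariates. That can fail when a score covariate is related both to a matching variable and to vaccination. Members of a matched pair then get different weights, and equality within pairs no longer gives equality between the weighted groups.

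Such covariates are plausible here. Comorbidity varies with maternal age. Complications recorded up to the index date have had longer to accrue when the index date falls later in pregnancy. Section 9.7.3.3 itself expects vaccinated and unvaccinated women to differ in health-seeking behaviour. Gestational age at entry bears on how much risk of spontaneous abortion, stillbirth or preterm birth remains. The weighted contrast could therefore be confounded by a factor the design had already controlled.

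**Working it through.** The protocol states no figure for this point, so there is none to reproduce. The check has three parts.

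**1. Exact calculation with one covariate.** From the protocol: the score is fitted in the matched set and omits the matching variable. Assumed, because the documents give no values: a binary matching variable (later or earlier gestational age at index, 50/50 in both groups after 1:1 matching); one binary score covariate Z, such as high utilization, with a given prevalence among unexposed women at later and earlier index; an odds ratio (OR) between Z and vaccination; and no vaccine effect.

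Strongest case, Z in 80% (later) and 30% (earlier) of unexposed women, OR 3:

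- Z among exposed women: later, odds 4 × 3 = 12, so 12/13 = 0.923; earlier, odds 0.4286 × 3 = 1.286, so 0.5625.
- Share of exposed with Z = 1: 0.5 × 0.923 + 0.5 × 0.5625 = 0.743; of unexposed: 0.40 + 0.15 = 0.55.
- Scores: e(Z=1) = 0.743/(0.743 + 0.55) = 0.575; e(Z=0) = 0.257/(0.257 + 0.45) = 0.364.
- Each arm's weights sum to 2. Weighted later-index share, exposed, weights 1/e: (0.4615/0.5746 + 0.0385/0.3637)/2 = 0.4545.
- Unexposed, weights 1/(1−e): (0.40/0.4254 + 0.10/0.6363)/2 = 0.5487.
- Standardized mean difference (SMD): (0.4545 − 0.5487)/√[(0.4545×0.5455 + 0.5487×0.4513)/2] = −0.19.

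If later index multiplies outcome risk by r, the null risk ratio becomes [1 + p₁(r−1)]/[1 + p₀(r−1)], where p₁ and p₀ are the weighted later-index shares in exposed and unexposed. For r = 2 this is 1.4545/1.5487 = 0.94; for r = 3, 1.909/2.097 = 0.91; for r = 0.25, 0.659/0.588 = 1.12.

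The same steps over a range of assumptions:

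| Z, later vs earlier (unexposed) | OR | SMD (absolute) | Null RR for r = 2 / 3 / 0.25 |
|---|---|---|---|
| 80% vs 30% | 3 | 0.19 | 0.94 / 0.91 / 1.12 |
| 70% vs 30% | 2 | 0.11 | 0.96 / 0.945 / 1.07 |
| 60% vs 40% | 1.5 | 0.04 | 0.99 / 0.98 / 1.02 |
| 50% vs 40% | 1.5 | 0.02 | 0.99 / 0.99 / 1.01 |
| 10% vs 1% | 1.5 | 0.02 | 0.99 / 0.99 / 1.01 |
| Z unrelated to gestational age, or OR 1 | – | 0 | 1 / 1 / 1 |

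**2. Several covariates, and the other matching variables.** With log odds of each covariate equal to −1 + 0.5·X + 0.5·A (X the matching variable, A exposure), the SMD on X is −0.03 for one covariate, −0.14 for five and −0.25 for ten. Reversing the sign on X gives +0.02 for one covariate, so the direction depends on the sign of the association. With X in the score it is 0 in every case.

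A simulation of 200,000 women, matched 1:1 in fine bins on age, calendar time and region (about 27,000 to 34,000 pairs), gave SMDs of at most 0.007 after matching. After weighting without those variables, the age SMD was 0.014 with no association, and −0.085, −0.181 and −0.195 as the association was strengthened. Calendar time reached −0.072 and region −0.020. With the variables in the score, no SMD exceeded 0.001 in absolute value.

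**3. Size against the planned precision.** Section 9.5.2 considers 20,000 women per group with 12% spontaneous abortion, about 4,800 events under the null, so the standard error of the log hazard ratio is about 2/√4,800 = 0.029 before any loss from weighting. A spurious 1.12 is ln(1.12)/0.029 = 3.9 standard errors; a spurious 1.01 is 0.3. For stillbirth (0.5%, 200 events) the standard error is 2/√200 = 0.141, and a spurious 0.91 is 0.7 standard errors.

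**The case against.** A reader might infer that weighting will undo the matching. The documents do not support that. The disturbance needs covariates related to both vaccination and a matching variable. The protocol gives none of those associations, and modest ones with a single covariate leave the risk ratio within about 2% of 1.

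A reader might also take the outcome model to be a marginal weighted one. Section 9.7.2 does not say so. It leaves open the time scale, stratification on matched set and adjustment for matching variables, and Section 9.7 defers detailed methods to the SAP. Stratifying on matched set would lessen the problem, and a Cox model on the gestational-age scale with delayed entry would compare women at the same gestational age.

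Nor would it be right to say that imbalance would go unseen: the Abstract and Section 9.7.2 both plan a balance check after weighting. And the gestational-age example does not extend to birth outcomes, which are indexed at LMP (Section 9.2.3).

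All of this limits the size and scope. What stands is that Table 7 itself fixes the content of the score, without the matching variables, and nothing the protocol states makes up for the omission. The balance check is not said to cover these variables, and no action follows if it fails. The gestational-age time scale would not by itself deal with maternal age, region or calendar time, which matter for birth outcomes too.

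**Conclusion.** The point holds as a risk that is cheap to remove. The score is fitted in the matched population without maternal age, region, LMP or gestational age at index, and weighting can therefore reintroduce imbalance on them. Under the assumed single-covariate associations the SMD lies between about 0.02 and 0.19, with a null risk ratio of 0.99 to 1.01 at the low end and 0.91 to 1.12 at the high end; it is zero without association. Several covariates acting in the same direction would add up. These figures are illustrative and rest on a weighted model with no matched-set conditioning or adjustment. At the planned sizes the upper end would matter for the common outcomes and the lower end would not.

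Separately, Section 9.1 and Table 7 contradict each other on whether gestational age at cohort entry is a matching variable.

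**What to change.** - In Table 7, mark maternal age, region, LMP interval and, for pregnancy outcomes only, gestational age at index as propensity-score covariates. Coarsen region if state is too sparse within a data partner, since analyses are first run separately by partner.
- Alternatively, state that the weighted outcome model conditions on matched set or adjusts for these variables.
- State in Section 9.7.2 that the planned post-weighting balance check includes them.
- Reconcile the blank matching cell for gestational age in Table 7 with Section 9.1.

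No new data are needed. The cost is a few more terms in the score and possibly slightly more variable weights.
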